**Table 7: Power calculations**

	Mean, intervention (st. dev.)	Difference from control	N intervention	N control	N total
	0,050	356	356	712	
A. Visual analog scale (VAS)	0,612 (0,238)	0,080	139	139	278
		0,105	87	87	174
		-2	908	908	1816
B. No. of consultation with GP	14,66 (15,21)	-3	404	404	808
		-4	227	227	454
		-0,5	1081	1081	2162
C. No. of outpatient consultations	2,34 (4,15)	-1	270	270	540
		-1,50	120	120	240
		-1,33	1371	1371	2742
D. No. of emergency inpatient days	4,14 (12,43)	-2,00	606	606	1212
		-2,50	388	388	776

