## 9. Statistical method and data analysis

### 9.1 Determination of sample size

The Norwegian Directorate of Health decided that 600 participants should be included in the trial, and the participating centers have committed to recruit patients according to this goal. This should not be regarded as a ceiling for how many patients can be recruited, and the centers have stated that they hope to recruit a larger number of participants. The sample size was decided by the Norwegian Directorate of Health prior to involvement from the research consortium, and power calculations were not used to calculate how many patients should be included in the trial.

The power calculations in Table 7, are based on the results of the previous trial of telehealth that was carried out by the NDH in 2016-2018 (Intro International, 2018). The trial investigated of the same endpoints, for a similar population. However, in the previous trial there was a greater spread in the degree of morbidity, but somewhat less spread in terms of diagnosis compared with the trial that is now being carried out. The number of users was also lower in the previous trial than we expected in this trial. Thus, there is some uncertainty associated with the reported standard deviations, and consequently, the calculations may overestimate the required sample size.

In Table 7, we focus on four outcome measures: self-assessed health status (VAS) from the EQ-5D questionnaire, number of regular GP consultations, number of outpatient consultations and number of bed-days in hospitals..

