From the previous trial, we know that after 5 to 9 months of telehealth follow-up, users reported self-rated health state at 0.612 (on a scale of 0 to 1), and this decreased by an average of 0.105 units from start-up. Thus, the users of medical distance monitoring experienced a decrease in self-assessed health status, but our hypothesis is that a control group would experience an even greater decline. In panel A, we show the required sample size to identify a statistically significant effect at a 5 % level with strength of 80 % for three different outcomes: that the action group reports 0.05, 0.08 or 0.105 lower reduction in self-assessed health status during the follow-up period compared to with the control group. In panel B, the desired sample size is calculated based on the number of GP consultations per year. In the previous trial, the participants experienced an average reduction of 2 visits per year compared to an average of 14.66 regular visits per year. We assume that the control group will be able to experience unchanged or increased number of GP consultations, and therefore calculate strength based on scenarios with a difference of 2-4 doctor visits. In panels C and D, the same calculations are repeated for the number of outpatient consultations and emergency days. The same reasoning applies.

Our assessment is that a sample size of 600 is enough to estimate significant effects of telehealth, but that a larger sample is preferable. The NDH and the participating municipalities are informed about this and work to increase the number of participants.

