## 9.2 Randomization

Patients who agree to participate in the trial are randomized 1: 1 to the intervention and control group. The treatment allocation is non-blinded in that both providers and patients will know the outcome of the treatment allocation. The actual randomization is carried out by a project employee in the local centers. The project administration stores sealed randomization envelopes in their office. Each sealed envelope contains a sheet marked with either "tiltak" (intervention) or "kontroll" (control), which determines which group the patient is placed in. For each GP in the trial, there is a separate stack of six envelopes: three "intervention" and three "control". Each time a patient on GP's X's list is invited to an information meeting, the project employee takes the top envelope from GP's stack of envelopes. If more than six patients are recruited on the GP's patient list, the project employee will receive a new stack of six envelopes for this GP. Thus, we can ensure that there will be approximately equal distribution of intervention and control patients from each GP. Oslo Economics distributes the stacks of opaque envelopes to the projects.

If a patient is invited to an information meeting and the patient's GP has not previously been involved in the trial, a separate stack of envelopes for this GP should be obtained prior to the meeting so that the patient can be randomized into the trial.

For each information meeting (chapter 8.3), the project employee takes an envelope from the appropriate GP's stack *without opening it*. The envelope is opened together with the patient after the consent form is signed, and the questionnaire is filled out. If the patient does not agree to participate in the trial, the envelope remains sealed. The project employee brings the sealed envelope back to the office and puts it back in the proper stack of envelopes.

 This randomization technique was considered the best practically implementable technique given the practical implementation of the study.

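### Table 7 has one wrong row (VAS 0.105: 81 per arm, not 87), and its service-count panels assume, without saying so, that the higher-use control arm has the intervention arm's SD

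*Combined protocol and SAP*

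**What the plan says.** Section 9.1 says that Table 7 shows the "required sample size to identify a statistically significant effect at a 5 % level with strength of 80" %. Patients "are randomized 1: 1 to the intervention and control group" (section 9.2). Each panel has a single mean and SD, headed "Mean, intervention (st. dev", and a column headed "Difference from control". For the three service counts the differences are negative, so the control arm is taken to use more.

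For GP visits the text says: "We assume that the control group will be able to experience unchanged or increased number of GP consultations". It continues: "In panels C and D, the same calculations are repeated for the number of outpatient consultations and emergency days", on the same reasoning. The GP mean is also described in another way: "the participants experienced an average reduction of 2 visits per year compared to an average of 14.66 regular visits per year". On the SDs, section 9.1 warns that they are uncertain and that "the calculations may overestimate the required sample size". It then judges 600 to be enough, while preferring more.

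**The concern.** There are two separate problems. First, one VAS row does not follow from the SD and difference printed beside it.

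Second, the service outcomes are non-negative counts whose SD exceeds the mean: 15.21 against 14.66, 4.15 against 2.34, and 12.43 against 4.14. In data of that shape the spread usually grows with the level. Holding the control SD at the intervention value while raising the control mean is then a favourable choice, and section 9.1 does not state it. What is at stake is how Table 7 reads against 600. Only five of its twelve scenarios have a printed total within 600: VAS 0.08 and 0.105, GP −4, and outpatient −1 and −1.5. Outpatient −1 has the least room.

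**Working it through.** **Inputs.** Means, SDs, differences and printed sizes come from Table 7. The 5% level and 80% power come from section 9.1, and 1:1 allocation from section 9.2. Sidedness is not stated, but two-sided reproduces the table. How the control SD relates to its mean is not in the documents, so it is an assumption here and is shown as a range.

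**Step 1: the plan's own figures.** With one SD in both arms, n per arm = 2 × (1.960 + 0.842)² × SD² / d² = 2 × 7.849 × SD² / d².

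- Panel A (SD 0.238): d = 0.05 gives 355.7 (printed 356) and d = 0.08 gives 138.9 (printed 139). For d = 0.105, 15.698 × 0.056644 / 0.011025 = 80.7, so 81 per arm and 162 in total. The printed 87 and 174 are wrong. Power at 87 per arm would be 82.9%.
- Panel B (SD 15.21): 907.9, 403.5, 227.0 (printed 908, 404, 227).
- Panel C (SD 4.15): 1081.4, 270.4, 120.2 (printed 1081, 270, 120).
- Panel D (SD 12.43): 1371.1, 606.3, 388.1 (printed 1371, 606, 388).

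All nine count rows reproduce with the printed SD in both arms.

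**Step 2: how far the control mean moves.** The largest scenarios are 4/14.66 = 27% (GP), 1.5/2.34 = 64% (outpatient) and 2.5/4.14 = 60% (emergency days).

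**Step 3: unequal SDs, taking the printed values as the intervention arm's.** n per arm = 7.849 × (SD_int² + SD_con²) / d². Power = Φ(d / √((SD_int² + SD_con²)/n) − 1.960). With intervention mean m, control mean m_c = m + |d| and r = m_c/m, four relations were tried:

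- (a) variance proportional to mean: SD_con = SD × √r
- (b) only the share of users changes: SD_con² = r(SD² + m²) − (rm)²
- (c) negative binomial with k = (SD² − m)/m²: SD_con² = m_c + k × m_c²
- (d) constant coefficient of variation: SD_con = r × SD

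Outpatient −1 (control mean 3.34, r = 1.427; totals are twice the unrounded n per arm):

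| Control SD | Value | Power at 270 per arm | Total for 80% | Power at 300 per arm |
|---|---|---|---|---|
| Common SD (Table 7) | 4.15 | 80% | 541 (printed 540) | 84% |
| (b) share of users | 4.61 | 75% | 604 | 80% |
| (a) variance ∝ mean | 4.96 | 72% | 656 | 76% |
| (c) negative binomial | 5.80 | 63% | 799 | 68% |
| (d) constant CV | 5.92 | 62% | 821 | 67% |

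Power at the printed sizes for all count rows, across the models:

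- Outpatient −0.5, −1, −1.5: 71–77%, 62–75%, 54–74%.
- Emergency days −1.33, −2, −2.5: 67–75%, 60–72%, 55–71%.
- GP −2, −3, −4: 74–77%, 72–76%, 69–75% under (a), (c) and (d). Under (b) it is 80–81%, because there the GP control SD falls slightly (14.83 at −4).

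GP −4 then needs 443–595 (printed 454) and outpatient −1.5 needs 277–444 (printed 240). Both stay within 600.

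**Step 4: break-even for outpatient −1 at 600.** 300 × 1² / 7.849 = 38.22. Subtracting 4.15² = 17.22 leaves 21.00, so SD_con may be at most 4.58, which is 4.58/4.15 = 1.10 times the printed SD.

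**Step 5: the other reading.** Suppose the printed values are levels before telehealth. Take the intervention mean as the printed mean minus the smallest listed difference. Section 9.1 states that reduction for GP visits (2 per year); for panels C and D it is an assumption. With the same four relations, power at the printed sizes is 79–85% for GP and 78–91% for emergency days. For outpatient −0.5, −1 and −1.5 it is 83–88%, 78–81% and 68–79%. Outpatient −1 needs 533–565, and outpatient −1.5 needs 249–319.

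**The case against.** A common SD is a normal planning convention, and panels B to D contain no arithmetic slip. A uniform shift in use would leave the SD unchanged, and the documents give nothing that fixes the control SD. This stands: a reader might infer that the printed sizes simply deliver 54–77% power, or that the outpatient scenario printed at 540 cannot fit within 600, but the documents support neither as fact. Both need the intervention label to be right and the control SD to follow its mean.

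Section 9.1 also leans the other way, since the previous trial had a wider spread of morbidity. With both SDs 10% smaller, outpatient −1 needs 532–666 under models (a) and (d). That caveat concerns the population, though, not the difference between arms, so it does not answer the point.

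Section 9.4 plans difference-in-difference and multilevel models, and registry data start in 2017. With an assumed baseline correlation of 0.5, adjustment would bring outpatient −1 to 494–618 under the same two models. Table 7 takes no such credit, and the correlation is not in the documents.

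Finally, 600 was set by the commissioning Directorate without a power calculation, use of services is a secondary outcome in Table 1, and the VAS slip is conservative. These limit the consequence. They do not make the table right.

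**Conclusion.** The VAS 0.105 row is a definite error that needs no outside assumption: 81 per arm and 162 in total, against 87 and 174.

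The shared SD in panels B to D is a favourable assumption that section 9.1 leaves unstated. Its effect is conditional. If the table heading is right, the outpatient and emergency-day rows fall below 80% power under all four relations and the GP rows under three. Outpatient −1 is then the only scenario that moves from within 600 to above it, with 67–80% power at 600 where the common SD implies 84%. If the printed values are pre-telehealth levels, that scenario fits within 600 and only outpatient −1.5 falls below 80% under every relation, still well within 600. Section 9.1 and the Table 7 heading do not settle which reading is meant.

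It does not follow that the trial needs more than 600 patients, or that any one dispersion model gives the correct totals.

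**What to change.** 1. Correct the VAS 0.105 row to 81 / 81 / 162.
2. Reconcile section 9.1 with the Table 7 heading: state which arm and period each mean and SD describe, for all three service counts.
3. Recompute panels B to D with SD_int² + SD_con² in place of twice one SD². Show the common-SD result beside a range for a control SD that rises with the mean, and label the relation as an assumption. Do not present one dispersion model as the right one.
4. If the intervention label stands, say in section 9.1 that outpatient −1 reaches 80% power at 600 only if the control SD is no more than about 10% above 4.15 (at most 4.58).

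The cost is one recalculated table and a short addition to section 9.1. Some stated sample sizes may look less favourable. No patients, visits or data are added.

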## 9.2 Randomization

Patients who agree to participate in the trial are randomized 1: 1 to the intervention and control group. The treatment allocation is non-blinded in that both providers and patients will know the outcome of the treatment allocation. The actual randomization is carried out by a project employee in the local centers. The project administration stores sealed randomization envelopes in their office. Each sealed envelope contains a sheet marked with either "tiltak" (intervention) or "kontroll" (control), which determines which group the patient is placed in. For each GP in the trial, there is a separate stack of six envelopes: three "intervention" and three "control". Each time a patient on GP's X's list is invited to an information meeting, the project employee takes the top envelope from GP's stack of envelopes. If more than six patients are recruited on the GP's patient list, the project employee will receive a new stack of six envelopes for this GP. Thus, we can ensure that there will be approximately equal distribution of intervention and control patients from each GP. Oslo Economics distributes the stacks of opaque envelopes to the projects.

If a patient is invited to an information meeting and the patient's GP has not previously been involved in the trial, a separate stack of envelopes for this GP should be obtained prior to the meeting so that the patient can be randomized into the trial.

For each information meeting (chapter 8.3), the project employee takes an envelope from the appropriate GP's stack *without opening it*. The envelope is opened together with the patient after the consent form is signed, and the questionnaire is filled out. If the patient does not agree to participate in the trial, the envelope remains sealed. The project employee brings the sealed envelope back to the office and puts it back in the proper stack of envelopes.

 This randomization technique was considered the best practically implementable technique given the practical implementation of the study.

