## 1.5 Participating municipalities and scope of the trial

The trial of telehealth is conducted at a total of six local centers. The participating centers are situated in the municipalities of Eid, Bodø, Larvik, Oslo (in the districts of Sagene, Grünerløkka, Gamle Oslo, St. Hanshaugen), Ullensaker (in cooperation with Gjerdrum) and Kristiansand. Kristiansand municipality is leading a local center recruiting patients from 30 municipalities in the Agder county.

Eid municipality, as well as a general practitioner office in Kristiansand and one in the Sagene district also participate in the pilot study of multidisciplinary care teams within primary care. The Norwegian Directorate of Health has asked the research consortium to evaluate synergies between the two trials. However, the telehealth trial is not designed to explicitly examine the effect of participating in both studies, as this was not possible within the frames given by the Norwegian Directorate of Health. Instead, synergies will be investigated through interviews.

The local centers carry out the trial in line with the guidelines from the Norwegian Directorate of Health. The centers also undertake to follow the study protocol for the trial. It is the centers' responsibility to recruit participants to the trial.

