# 5. Recruitment of study participants

Potential participants are first proposed by health personnel at hospitals or in municipal health and care services, by GPs, by patients themselves or their relatives, either directly to the patient's GP or to the project administration (possibly via the municipal allocation office) (step 1 in Figure 3). Participation proposals are forwarded from the project administration to the GP. Then, the GP, who has the medical responsibility for the patients on their patient list (i.e., within the GP scheme), is responsible for deciding whether the patient is eligible for receiving telehealth (step 2). In cases where the GP receives proposals directly, the GP makes this assessment immediately. If a patient is considered eligible, the patient is invited to an information meeting with a project employee where the patient is offered the opportunity to participate in the trial (step 3). If the patient gives her consent to participate in the trial, the patient is randomized into an intervention or a control group (step 4). Randomization takes place in connection with the information meeting, and the project administration is responsible for the randomization. Thereafter, the patient receives further follow-up depending on which group they are allocated to (step 5).

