### **5.2 Step 2: The GP assesses eligibility**

The Norwegian Directorate of Health has planned that approximately 100 GPs will participate in the trial. The centers have signed letters of intent with GPs who are committed to recruiting patients for the trial. The GP has the medical responsibility for the patients on their list and should therefore assess the patient's eligibility for telehealth (i.e., whether the patient meets the inclusion criteria) based on their knowledge of the patient, patient records and the information in the proposal message from the project administration or other health personnel.

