### **5.3 Step 3: Patients are invited to participate in the trial**

Patients who have been deemed eligible for participation by the GP will be contacted by the project administration and invited to an individual meeting where the patient is invited to participate in the trial. The information meeting can be held at the project employee's workplace, or at the patient's home if necessary due to the patient's health condition. At the information meeting, the project employee will inform the patient about the trial and about telehealth. The meeting will include:

- Information about the trial and what participation means for the patient. The Norwegian Directorate of Health and the centers have prepared information material (a brochure and an information film) that can be used as a basis for the discussion.
- Obtaining consent for participation (see details below)
- Completion of a questionnaire about her physical and mental health, follow-up from and experiences with the health and care service, and background information, including demographics, marital status, place of residence and housing, scope of informal care from family and friends, use of other types of welfare technology (security alarm, self-help tools, etc.).
- Randomization into intervention or control group (see section 5.4)
- Information on further follow-up (see section 5.5)

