### Obtaining consent for participation

After the project employee has informed the patient about the trial and what the participation entails, the patient is asked whether he / she agrees to participate in the trial. If the patient agrees to participate in the trial, the patient signs the consent form. A requirement for participation is that the patient is competent for consent. Relatives cannot consent on behalf of the patient. The patient cannot receive telehealth without the consent to participate in the trial.

If the patient does not agree to participate in the trial, the meeting ends, and the patient is followed up further by the healthcare service according to standard clinical care. In this case, the patient will not be able to receive telehealth, and patient information is not recorded as part of the trial. However, anonymous information is registered to inform the analysis of loss-to-follow-up (see section 9.5). If the patient does not agree to participate in the trial, the randomization envelope is not opened, and the project employee brings the unopened envelope back to the office and place it back in the stack of envelopes.

If the patient needs more time before he / she decides whether to participate or not, the patient may have a reflection period of a maximum of two weeks. Equipment for the use of telehealth cannot be delivered to the patient before the patient has signed the consent statement for participation in research.

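### Fixed, disclosed stacks of three plus three envelopes per GP let staff who keep track deduce some allocations before the consent talk

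*Combined protocol and SAP*

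**What the plan says.** Section 9.2 describes the allocation: "For each GP in the trial, there is a separate stack of six envelopes", three marked intervention and three marked control. A GP who recruits more than six patients gets another stack of six. Allocation is not blinded. On custody, the same section says: "The project administration stores sealed randomization envelopes in their office".

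The project employee takes the top envelope from that GP's stack for each meeting. Section 5.3 adds: "At the information meeting, the project employee will inform the patient about the trial and about telehealth". The envelope is opened with the patient after consent and the baseline questionnaire (section 5.4). If the patient declines, "the project employee brings the unopened envelope back to the office and place it back in the stack of envelopes" (section 5.3). The project administration records each participant's group and the recruitment dates (section 8.2).

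The composition of the stacks is not hidden from the centers. It is written in the protocol, and section 1.5 states: "The centers also undertake to follow the study protocol for the trial".

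The stated safeguards are sealed, opaque envelopes distributed by the evaluator, opening only after consent and questionnaire, and an eligibility decision by the GP, who "is responsible for deciding whether the patient is eligible for receiving telehealth" (section 5). A footnote to section 9.2 adds: "This randomization technique was considered the best practically implementable technique given the practical implementation of the study".

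**The concern.** A sealed envelope cannot be read, but its content can be deduced. In an open trial with a fixed and known composition, once three envelopes of one kind have been opened, every envelope left in that stack is known. The person who can work this out also informs the patient and asks for consent.

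An employee who knows the next arm could, even without intent, schedule, inform or encourage a patient differently. The arms could then differ in who agrees to take part.

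The planned data allow only a partial check. Register use is available for at least two years before recruitment (section 6.3). For randomized patients, the group, the dates and the GP largely give the order within a stack. Refusals cannot be placed: their anonymous record holds gender, age group, main diagnosis, recruitment channel and reason, but no GP or envelope (sections 8.2 and 9.5).

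The analysis would not reliably remove a baseline difference either. A comparison of changes is fixed for EQ-5D (section 6.1). Difference-in-difference models are promised only for some variables (section 9.4), so nothing fixes such a comparison for satisfaction or cost.

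**Working it through.** The documents give no predictability figure to reproduce.

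**Inputs.** Stack of 3 + 3 (section 9.2); 600 patients (section 9.1); "approximately 100 GPs will participate in the trial" (section 5.2), with further GPs foreseen (sections 5.2 and 9.2).

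**Assumptions.** All C(6,3) = 20 orders are equally likely; the documents do not say how stacks are ordered. Each envelope is opened before the next talk.

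**One completed stack.** An allocation is certain when one arm is used up.
- Positions 1 to 3: 0.
- Position 4: the first three alike, 2/20 = 0.10.
- Position 5: three of one kind among four, 2·C(3,3)·C(3,1)/C(6,4) = 6/15 = 0.40.
- Position 6: 1.00.
- Sum 1.5; 1.5/6 = 25%. Of the 20 orders, 12 give one certain allocation, 6 give two and 2 give three.

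Best guess (the arm with more envelopes left), by position: 0.5 + 0.6 + 0.6 + 0.7 + 0.7 + 1.0 = 4.1; 4.1/6 = 68.3%.

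**Overlapping talks.** Envelopes are taken per invitation, and a patient may take up to two weeks to decide (section 5.3). If one earlier envelope is always still unopened, each probability moves one place later: 0.10 + 0.40 = 0.5; 0.5/6 = 8.3%.

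**Trial-wide.** The expected number of certain allocations for a GP with k patients is f(k) = 0 for k up to 3, then 0.1, 0.5 and 1.5 for k = 4, 5, 6; 1.5 for k = 7 to 9; 1.6 for k = 10. The pattern repeats with 1.5 added per full stack.
- Exactly six per GP: 1.5/6 = 25%, the maximum.
- Minimum at a mean of six: f(k) is never below 0.25k − 0.9, so the mean is at least 1.5 − 0.9 = 0.6, and 0.6/6 = 10%. This is met with two thirds of GPs at four patients and one third at ten: (2/3)(0.1) + (1/3)(1.6) = 0.6.
- 0% needs no GP above three patients: 600/3 = 200 GPs or more.
- Assumed Poisson counts with means of six, three and two: 16.2%, 6.4%, 2.6% (about 97, 39 and 16 of 600).
- Assumed uneven counts (negative binomial, dispersion 1): 17.6%, 12.3%, 8.8%.

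**With block sizes 6 and 8, equally likely.** The guesser is assumed to know the two sizes but not which was drawn. Among a GP's first six patients, an allocation is certain only if the block is of size 8 and four of one kind are out.
- Position 5: ½ · 2/70 = 0.0143.
- Position 6: ½ · 2·C(4,1)/C(8,5) = ½ · 8/56 = 0.0714.
- Sum 0.0857; 0.0857/6 = 1.4%.

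Simulated results:

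| | Fixed 6 | 6 and 8 |
|---|---|---|
| Best guess, first six | 68.3% | 64.3% |
| Certain, Poisson 6 / 3 / 2 | 16.2 / 6.4 / 2.6% | 3.2 / 0.6 / 0.2% |
| Best guess, Poisson 6 / 3 / 2 | 64.3 / 59.6 / 57.0% | 62.8 / 58.1 / 55.9% |

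Sizes 4, 6 and 8 reduce certainty slightly more (1.0% over the first six). They raise the best guess when GPs recruit few patients: 59.6% to 60.1% at mean three and 57.0% to 57.7% at mean two. That is the reason to leave out 4.

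**The case against.** The strongest reply has four parts.

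First, nothing shows that staff track stacks. That stands: the documents establish an opportunity only.

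Second, safeguards exist. The GP decides eligibility before the employee meets the patient, all patients found eligible are to be contacted, and a brochure and film can be used as the basis for the talk (section 5.3). Sensitivity analyses with control variables (section 9.4) and register-based comparison groups (sections 9.3 and 11) are planned. These narrow the employee's room to scheduling, informing and encouraging. They do not hide what is left in a stack.

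Third, the technique was chosen deliberately, for near-equal arms within each GP, and the footnote calls it the best practicable one. That can justify paper envelopes and local opening. It gives no reason for a fixed and disclosed block size, since varying blocks use the same envelopes and staff.

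Fourth, the remedy mainly removes certainty. The best guess over a GP's first six falls only from 68.3% to 64.3%, and a good guess can also influence behavior. This stands and limits the urgency. Central release after consent would do more, but it would change the procedure the footnote defends.

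A reader might infer that a quarter of all allocations in this trial are known in advance, or that the comparison is biased. The documents support neither. The 25% applies to completed stacks opened strictly in sequence, and the trial-wide share depends on recruitment per GP, which the documents do not give.

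**Conclusion.** The concern holds as a conditional weakness in allocation concealment. If staff keep track, and stacks are randomly ordered and opened in sequence, they would know on average 25% of a completed stack before the consent talk. With one earlier envelope always unopened, the figure is 8.3%. For 600 patients over exactly 100 GPs the sequential figure is 10% to 25%, about 16% with Poisson counts. It is lower if many further GPs join, and zero only with at least 200 GPs and none above three patients. The Poisson and negative binomial counts are assumptions, not figures from the plan. If stacks were not randomly ordered, predictability could be higher.

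The size of any bias cannot be derived, and none is claimed. Priority lies between optional and recommended: the exposure is unproven, but the remedy is standard and cheap.

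**What to change.** Have the evaluator that distributes the stacks prepare, for each GP, a sequence with randomly varying block sizes (for example 6 and 8, without 4). The sizes should not be disclosed to centers or GPs, and the sequence should be supplied in sequentially numbered opaque envelopes. Use it for all new GPs and all later stacks. Refusers' envelopes return to their numbered place.

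Exchanging unused envelopes in current stacks is optional. Without it, GPs who already hold a stack keep most of their certain allocations: about 95% at Poisson mean six. Under uneven recruitment with the same mean the figure is about 64% if later stacks use sizes 4, 6 and 8 (0.113/0.176), and about 69% in a simulation run for this note with sizes 6 and 8.

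Record the envelope number for every envelope taken to a meeting, including those for refusers, in the anonymous refusal record if privacy rules allow. A returned envelope is opened by a later patient, so the number shows afterwards which arm the refuser would have had. Selective refusal can then be checked.

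**Cost.** An amendment under section 10.4 and new envelopes, with the same paper method and staff. GP-level imbalance can reach 4 instead of 3 for new GPs. With sizes 6 and 8, a block of eight starts with four alike with probability 2/70 = 0.0286. The chance of reaching 4 within a GP's first 12 patients is then ½(0.0286 + 0.9714·½·0.0286) + ½·½·0.0286, about 2.8%. Exchange adds logistics at six centers, one recruiting from 30 municipalities (section 1.5), and its worst-case imbalance is 3 + 4 = 7.
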